#### **8.6.2.4 Week 8 (Visit 6)**

The Week 8 visit (Visit 6) will take place on Day 57 ± 2 calendar days relative to the start of study medication intake.

- Any remaining study medication as well as empty study medication containers will be returned to the investigator, and an accountability check will be performed.
- Any AEs that have occurred since signing the ICF will be documented, and any changes in concomitant medication will be reported.
- Vital signs will be measured.
- The subject diary card will be collected, a summary will be recorded in the eCRF, and a new subject diary card will be dispensed.

CONFIDENTIAL

- Serum CRP will be measured.
- SJC66 and TJC68 evaluations will be performed.
- Physician's and Patient's Global Assessments of Disease Activity will be completed.
- The subject will complete the HAQ-DI.
- Hematology, clinical chemistry, and urinalysis (dipstick and microscopy) tests will be performed on samples collected at this visit. A urine pregnancy test will be performed on females of childbearing potential.

When all of these procedures have been performed, the study medication will be dispensed according to the information provided using IXRS and the date of the next visit will be confirmed.

#### **8.6.2.5 Week 12 (Visit 7)**

The Week 12 visit (Visit 7) will take place on Day 85 ± 2 calendar days relative to the start of study medication intake.

- Any remaining study medication as well as empty study medication containers will be returned to the investigator, and an accountability check will be performed.
- Any AEs that have occurred since signing the ICF will be documented and any changes in concomitant medication will be reported.
- Vital signs will be measured.
- A 12-lead ECG will be performed.
- A physical examination will be performed.
- The subject diary card will be collected, a summary will be recorded in the eCRF, and a new subject diary card will be dispensed.
- Blood samples for measurement of PK and PD parameters will be collected.
- Serum CRP will be measured.
- SJC66 and TJC68 evaluations will be performed.
- Physician's and Patient's Global Assessments of Disease Activity will be completed.
- The subject will complete the HAQ-DI.
- The subject will complete the FACIT fatigue scale and SF-36 questionnaire.
- Hematology, clinical chemistry, and urinalysis (dipstick and microscopy) tests will be performed on samples collected at this visit. A urine pregnancy test will be performed on females of childbearing potential.

At Visit 7, all subjects on placebo and the subjects on the 50 mg dose who have not achieved a 20% improvement in SJC66 and TJC68 will be assigned (automatically via IXRS) to 100 mg q.d. in a blinded fashion and will continue the study until Week 24. Subjects in the other groups will maintain their randomized treatment until Week 24.

When all of these procedures have been performed, the study medication will be dispensed according to the information provided using IXRS and the date of the next visit will be confirmed.

#### **8.6.2.6 Week 16 (Visit 8)**

The Week 16 visit (Visit 8) will take place on Day 113 ± 2 calendar days relative to the start of study medication intake.

- Any remaining study medication as well as empty study medication containers will be returned to the investigator, and an accountability check will be performed.

CONFIDENTIAL

- Any AEs that have occurred since signing the ICF will be documented and any changes in concomitant medication will be reported.
- Vital signs will be measured.
- The subject diary card will be collected, a summary will be recorded in the eCRF, and a new subject diary card will be dispensed.
- Serum CRP will be measured.
- SJC66 and TJC68 evaluations will be performed.
- Physician's and Patient's Global Assessments of Disease Activity will be completed.
- The subject will complete the HAQ-DI.
- Hematology, clinical chemistry, and urinalysis (dipstick and microscopy) tests will be performed on samples collected at this visit. A urine pregnancy test will be performed on females of childbearing potential.

When all of these procedures have been performed, the study medication will be dispensed according to the information provided using IXRS and the date of the next visit will be confirmed.

#### **8.6.2.7 Week 20 (Visit 9)**

The Week 20 visit (Visit 9) will take place on Day 141 ± 2 calendar days relative to the start of study medication intake.

- Any remaining study medication as well as empty study medication containers will be returned to the investigator, and an accountability check will be performed.
- Any AEs that have occurred since signing the ICF will be documented and any changes in concomitant medication will be reported.
- Vital signs will be measured.
- The subject diary card will be collected, a summary will be recorded in the eCRF, and a new subject diary card will be dispensed.
- Serum CRP will be measured.
- SJC66 and TJC68 evaluations will be performed.
- Physician's and Patient's Global Assessments of Disease Activity will be completed.
- The subject will complete the HAQ-DI.
- Hematology, clinical chemistry, and urinalysis (dipstick and microscopy) tests will be performed on samples collected at this visit. A urine pregnancy test will be performed on females of childbearing potential.

When all of these procedures have been performed, the study medication will be dispensed according to the information provided using IXRS and the date of the next visit will be confirmed.

#### **8.6.2.8 Week 24 (Visit 10) or Early Discontinuation Visit**

The Week 24 visit (Visit 10) will take place on Day 169 ± 2 calendar days relative to the start of study medication intake. Subjects who have discontinued from the study early and subjects who attend the Week 24 visit will complete the following assessments. This visit needs to be entered in IXRS.

- Any remaining study medication as well as empty study medication containers will be returned to the investigator, and an accountability check will be performed.
- Any AEs that have occurred since signing the ICF will be documented and any changes in concomitant medication will be reported.

- Vital signs will be measured.
- A 12-lead ECG will be performed.
- A physical examination will be performed.
- The subject diary card will be collected and a summary will be recorded in the eCRF.
- Blood samples for measurement of PK and PD parameters will be collected.
- Serum CRP will be measured.
- SJC66 and TJC68 evaluations will be performed.
- Physician's and Patient's Global Assessments of Disease Activity will be completed.
- The subject will complete the HAQ-DI.
- The subject will complete the FACIT fatigue scale and SF-36 questionnaire.
- Hematology, clinical chemistry, and urinalysis (dipstick and microscopy) tests will be performed on samples collected at this visit. A serum pregnancy test will be performed on females of childbearing potential.

### **8.6.3 Follow-up (Visit 11)**

A Follow-up visit (Visit 11) will be performed only for subjects discontinuing prematurely from the study and for subjects not entering the LongTerm Follow-up Study GLPG0634-CL-205. This will take place 7 to 10 calendar days after either the EDV or the Week 24 visit.

- Any AEs that have occurred since signing the ICF will be documented and any changes in concomitant medication will be reported.
- Vital signs will be measured.
- A 12-lead ECG will be performed.
- A physical examination will be performed.
- Hematology, clinical chemistry, and urinalysis (dipstick and microscopy) tests will be performed on samples collected at this visit. A urine pregnancy test will be performed on females of childbearing potential.

### **8.6.4 Duration of Treatment**

Subjects participating in the study will be requested to attend a total of 11 visits throughout the study: Screening visit (up to 28 calendar days before Baseline visit), Baseline visit, Week 1 visit, Week 2 visit, Week 4 visit, Week 8 visit, Week 12 visit, Week 16 visit, Week 20 visit, Week 24 visit, and for the subjects not entering the Long Term Follow-up study (GLPG0634-CL-205), a Follow-up visit 7 to 10 calendar days after end of study treatment.

Consequently, each subject will remain in the study for approximately 29 weeks (from Screening visit to Follow-up visit). Treatment will last for 24 weeks.

## **8.7 Efficacy, Pharmacokinetics, Pharmacodynamics, and Safety Variables**

The flow chart in Section 8.7.1.5 shows the planned study assessments.

## **8.7.1 Efficacy, Pharmacokinetics, Pharmacodynamics and Safety Measurements Assessed and Flow Chart**

### **8.7.1.1 Efficacy Assessments**

#### **8.7.1.1.1 Evaluation of Disease Activity**

Efficacy assessments will be carried out at Screening (joint counts and Patient's Global Assessment of Disease Activity only); Baseline (Day -1); Weeks 1, 2, 4, 8, 12, 16, 20, and 24; and the EDV (if applicable).

Each of 68 joints will be evaluated for tenderness, and each of 66 joints will be evaluated for swelling (Appendix 13.2).

A joint assessor with adequate training and experience in performing joint assessments will be designated at each study site to perform all joint assessments. The joint assessor should preferably be a rheumatologist; however, if a rheumatologist is not available, it should be a health care worker with at least one year's experience in performing joint assessments. The assessor should remain the same throughout the study per subject, as much as possible. It is required that the designated joint assessor identify an appropriate back-up assessor to provide coverage if the designated joint assessor is absent.

#### **8.7.1.1.2 Patient's Global Assessment of Disease Activity**

The Patient's Global Assessment of Disease Activity will be recorded on a 0 to 100 visual analog scale (VAS), with 0 indicating "very well" and 100 indicating "very poor" in answer to the question "Considering all the ways arthritis affects you, how well are you doing today?" (Appendix 13.3).

#### **8.7.1.1.3 Physician's Global Assessment of Disease Activity**

The Physician's Global Assessment of Disease Activity will be recorded on a 0 to 100 mm VAS, with 0 indicating "no disease activity" and 100 indicating "extreme disease activity". The evaluating physician and the subject must complete the global assessments independently of each other (Appendix 13.4).

#### **8.7.1.1.4 Health Assessment Questionnaire - Disability Index (HAQ-DI)**

The functional status of the subject will be assessed using the HAQ-DI. This 20-question instrument assesses the degree of difficulty a person has in accomplishing tasks in 8 domains (dressing, arising, eating, walking, hygiene, reaching, gripping, and errands/chores). Responses are scored on a 4-point Likert scale from 0, indicating no difficulty, to 3, indicating inability to perform a task in that area. The need for aids/devices or help from another person will also be recorded. The HAQ-DI total score ranges from 0 to 3 with higher scores indicating greater dysfunction (Appendix 13.5).

As part of the HAQ-DI, subjects will be asked to assess their average pain during the last week on a 0 to 100 mm VAS, with 0 indicating "no pain" and 100 indicating "severe pain". This assessment should be completed before the joint examination. This pain score will be used to drive the ACR20/50/70.

#### **8.7.1.1.5 FACIT Fatigue Scale**

The FACIT fatigue scale (version 4) measures an individual's level of fatigue during their usual daily activities over the past week. It consists of 13 questions with a 7-day recall period on a 5-point Likert scale, with 0 indicating "not at all" and 4 indicating "very much". The total score ranges from 0 to 52. The higher the score, the better the quality of life (Appendix 13.6).

#### **8.7.1.1.6 36-Item Short-form Health Survey (SF-36)**

The health-related quality of life of the subject will be assessed using the SF-36 (version 2) with a 4-week recall period. This consists of 36 questions belonging to 8 domains in 2 components:

- Physical well-being: 4 domains: physical functioning (10 items), role physical (4 items), bodily pain (2 items), and general health perceptions (5 items).
- Mental well-being: 4 domains: vitality (4 items), social functioning (2 items), role emotional (3 items), and mental health (5 items).

The remaining item (health transition) is not part of the above domains but is kept separately (Appendix 13.7).

These scales will be rescaled from 0 to 100 (converting the lowest possible score to 0 and the highest possible score to 100), with higher scores indicating a better quality of life.

#### **8.7.1.2 Pharmacokinetic Assessments**

One blood sample (2 mL) for analysis of GLPG0634 and its metabolite (G254445) in plasma will be collected at Weeks 4, 12, and 24 or the EDV, if applicable, by venipuncture (or indwelling cannula) in the forearm into tubes containing lithium heparin and will be immediately chilled (ice bath), processed, and frozen as plasma at -20°C (-4°F).

#### **8.7.1.3 Pharmacodynamic Assessments**

Blood samples for PD assessments will be collected in all subjects at Baseline (Day -1), Week 1, Week 4, Week 12 and Week 24 or the EDV, if applicable.

Two blood samples of 2.5 mL each will be collected in 2 PAX-gene tubes. Immediately after collection, the tubes will be gently inverted 8 to 10 times and stored at room temperature for a minimum of 2 hours and a maximum of 72 hours before freezing at -20°C (-4°F) for storage until further analysis (gene expression in circulating leukocytes and messenger ribonucleic acid as well as micro ribonucleic acid [miRNA] profiling).

Additionally, 1 blood sample of 8.5 mL will be collected in a SST tube. The sample will be allowed to clot in the tube for 30 minutes at room temperature, after which the tube will be centrifuged. Serum will be extracted, divided over 4 aliquots, and frozen at -80°C (-112°F) until further analysis (analytes and miRNA profiling).

#### **8.7.1.4 Safety Assessments**

##### **8.7.1.4.1 Adverse Event Definitions and Reporting**

###### **8.7.1.4.1.1 Definitions**

ICH and European guidance will be followed for AE reporting.

###### **Adverse Event**

An AE is any untoward medical occurrence in a clinical study subject administered a medicinal (investigational or noninvestigational) product. An AE does not necessarily have a causal relationship with the treatment. An AE can therefore be any unfavorable and unintended sign (including an abnormal finding), symptom, or disease temporally associated with the use of a medicinal (investigational or noninvestigational) product, whether or not related to that medicinal (investigational or noninvestigational) product.

This includes any occurrence that is new in onset or aggravated in intensity or frequency from the baseline condition (signing the ICF) or abnormal results of diagnostic procedures, including laboratory test abnormalities.

###### **Serious Adverse Event**

A SAE is any untoward medical occurrence that at any dose meets any of the following conditions:

- results in death.
- is life-threatening: the subject is at risk of death at the time of the event. It does not refer to an event that hypothetically might cause death if it were more severe.
- requires inpatient hospitalization or prolongation of existing hospitalization.
- results in persistent or significant disability or incapacity.
- is a congenital anomaly or birth defect.
- is a medically significant event that may not be immediately life-threatening or result in death or hospitalization but may jeopardize the subject or may require intervention to prevent one of the other outcomes listed in the definitions above.

###### **Unexpected Adverse Event/Reference Safety Information**

An AE is considered unexpected if the nature or intensity is not consistent with the applicable product reference safety information. For an investigational product, the expectedness of an AE will be determined by whether or not it is listed in the IB.

###### **Intensity of an Adverse Event**

Each AE must be rated on a 3-point scale of increasing intensity:

- Mild: Transient or mild discomfort; no limitation in activity; no medical intervention/therapy required.
- Moderate: Mild to moderate limitation in activity; some assistance may be needed; no or minimal medical intervention/therapy required.
- Severe: Marked limitation in activity; some assistance usually required; medical intervention/therapy required, hospitalization possible.

If there is a change in intensity of an ongoing AE, it must be recorded as a separate event.

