12.1. ADVERSE EVENTS

12.1.1. Treatment-Emergent Principle

All adverse events with onset on or after first dosing are considered treatment-emergent adverse events (TEAE).

Adverse events will be placed into analysis periods according to their start date. Analysis periods: see section 3.2. The AE will only be presented in the analysis period during which it started. Rule: period start date \leq AE start date \leq period stop date.

In case the AE start date is incomplete, a worst-case allocation will be done according to the available parts of the AE start date. When too much of the AE start date is missing to apply the above rules, the AE will be allocated to:

- the first treatment period, in case the doubt is between the screening and first treatment analysis period;
- both treatment periods, in case the doubt is between both treatment periods.

All adverse events emerging during the screening period will only be listed, not presented in any of the tables. These events are not TEAEs. All tables will present TEAEs only.

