12.1.3. Worst-Case Principle

When cross-tabulating AE preferred terms versus an AE attribute (e.g., intensity), the worst-case is always applied within each analysis period. I.e., when a subject has two times the same AE preferred term in the same analysis period, then the subject is reported only once: only with the worst intensity. If this happens in two different analysis periods, the AE is reported twice: once in each analysis period.

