12.1.7. Tables over the whole 24 weeks period

The same tables will be created for the full 24 weeks period of the study, using the 5 groups as specified in section 2.4.

All tables will be created for 3 analysis periods: “first 12 weeks”, “second 12 weeks”, and “full 24 weeks” as defined in section 3.2.

Population: Safety.

Table 14.3.1.16: Treatment-emergent adverse events over the whole study: Summary table

Tabulation per treatment of the number and percentage of subjects with the following:

- Subjects with at least one treatment-emergent adverse event (TEAE)
- Subjects with at least one serious TEAE
- Subjects who died (treatment-emergent)
- Subjects with at least one mild TEAE as worst intensity
- Subjects with at least one moderate TEAE as worst intensity
- Subjects with at least one severe TEAE
- Subjects with at least one TEAE that was considered treatment-related
- Subjects with at least one treatment-emergent SAE that was considered treatment-related
- Subjects with at least one TEAE for which the study treatment was temporarily stopped
- Subjects with at least one TEAE for which the study treatment was permanently stopped
- Subjects with at least one TEAE flagged as an individual stopping criterion by the investigator
- Subjects with at least one TEAE that has not resolved.

Population: safety.

Table 14.3.1.17: Treatment-emergent adverse events over the whole study: Summary table by region

(only for the “full 24 weeks”, not for the two periods separately)

Table 14.3.1.18: Treatment-emergent adverse events over the whole study: Tabulation of all adverse events

Table 14.3.1.19: Treatment-emergent adverse events over the whole study: Tabulation of all adverse events by region

(only for the “full 24 weeks”, not for the two periods separately)

Table 14.3.1.20: Treatment-emergent adverse events over the whole study: Tabulation of all adverse events by gender

(only for the “full 24 weeks”, not for the two periods separately)

Table 14.3.1.21: Treatment-emergent adverse events over the whole study: Tabulation of all adverse events by age category

(only for the “full 24 weeks”, not for the two periods separately)

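### As written, an adverse event that only improves across first dose or across the Week 12 visit is tabulated as a new treatment-emergent event

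*Protocol*

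**What the plan says.** Protocol 8.7.1.4.1.1, under Intensity of an Adverse Event, rates each AE as mild, moderate or severe and adds: "If there is a change in intensity of an ongoing AE, it must be recorded as a separate event". A fall from moderate to mild is covered as much as a rise. The AE definition in the same section mentions something "new in onset or aggravated in intensity or frequency from the baseline condition", which points to onset or worsening. Collection starts at signature of the consent form (Protocol 8.7.1.4.1.2), so an AE can already be on record and ongoing at first dose.

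SAP 12.1.1 sets treatment emergence by date: "All adverse events with onset on or after first dosing are considered treatment-emergent adverse events (TEAE". Periods follow the same logic: "Adverse events will be placed into analysis periods according to their start date", and "The AE will only be presented in the analysis period during which it started". SAP 3.2 ends the first period on the date of the Week 12 visit and starts the second on the next day. AEs that start in screening are listed but not tabulated.

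SAP 12.1.3 handles repeats of a preferred term. Within one period, "then the subject is reported only once: only with the worst intensity". Across periods the rule is different: "If this happens in two different analysis periods, the AE is reported twice: once in each analysis period". SAP 12.1.7 adds: "All tables will be created for 3 analysis periods: “first 12 weeks”, “second 12 weeks”, and “full 24 weeks” as defined in section 3.2". The 24-week columns are the five treatment sequences of SAP 2.1.2.

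**The concern.** The recording rule and the classification rule do not fit together. One produces a record whenever intensity changes in either direction. The other treats every record dated after first dose as emerging on treatment. Nothing links a record to the event it continues, and nothing asks whether the subject is worse than before.

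Elsewhere the SAP does compare with baseline. CTCAE laboratory grades and ATP III classes must be higher than at baseline (12.2.9, Tables 14.3.2.8 and 14.3.2.11), and so must QT categories (12.3.6, Table 14.3.3.4). The normal-range laboratory and vital-sign tables at least require a difference from baseline. The AE rule has no such comparison.

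The design makes boundary cases foreseeable. Screening lasts up to 28 days and includes methotrexate washout for subjects taking it (Protocol 8.6.1.1). Changes in concomitant illness before Baseline are documented as AEs (8.6.1.2). At Week 12 all placebo subjects and the 50 mg non-responders move to 100 mg.

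At stake is the descriptive safety comparison by dose. Tables 14.3.1.1, 14.3.1.3 and 14.3.1.7 are also specified for the Week 12 interim analysis, which is meant to support phase III dose selection.

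**Working it through.** The plan states no figure for this point, so there is nothing to reproduce. The check traces the written rules.

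**Inputs.** First dose is Day 1 and the Week 12 visit is taken at its target, Day 85 (SAP 3.1 and 3.3). Periods come from SAP 3.2, emergence and allocation from 12.1.1, and de-duplication from 12.1.3. Each arm has 70 subjects (Protocol 8.5.4). One assumption is needed: the separate record starts on the day the intensity changed.

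**Trace, one subject and one preferred term.**

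| Course | First 12 weeks | Second 12 weeks | Full 24 weeks |
|---|---|---|---|
| A. Moderate from Day -10, mild from Day 5 | 1 (mild) | 0 | 1 (mild) |
| A0. Moderate from Day -10, no change | 0 | 0 | 0 |
| B. Moderate from Day 40, mild from Day 60 | 1 (moderate) | 0 | 1 (moderate) |
| C. Moderate from Day 70, mild from Day 95 | 1 (moderate) | 1 (mild) | 1 (moderate) |
| C0. Moderate from Day 70, no change | 1 (moderate) | 0 | 1 (moderate) |

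A against A0: the subject who improves has a TEAE and the subject who does not improve has none. C against C0: improvement adds an entry in the second period only. B: no extra count, because the within-period rule keeps one entry at the worst intensity.

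**Size per affected subject.** The added incidence in a preferred-term row is m / n for m affected subjects in a column of n. With n = 70:
- 1/70 = 1.43 percentage points
- 3/70 = 4.29 points
- 5/70 = 7.14 points

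These values of m are illustrations. After Week 12 the 50 mg arm is split into two sequence columns, so n is smaller there. With an even split (an assumption), 1/35 = 2.86 points.

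The any-TEAE row rises only if the subject has no other TEAE. If half of affected subjects have another (an assumption), the expected addition per affected subject is 0.5 x 1.43 = 0.71 points.

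**After the fix.** Case A gives 0 TEAEs instead of 1. Case C gives 0 second-period entries instead of 1. Case B is unchanged.

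**The case against.** Much of the opposing case stands, and it limits the point.

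- **Within-period changes.** A reader might infer that every intensity change inflates the tables. It does not. The tables count subjects, and case B adds nothing. Only an AE still ongoing across first dose or across Week 12 matters, and only if it was moderate or severe, since a mild AE on this three-point scale cannot fall in grade without resolving.
- **The Week 12 route.** A reader might infer that placebo or 50 mg events move into the 100 mg column. They do not. The switched subjects have their own sequence columns, separate from the continued 100 mg group. The full-24-week tables count such an event once, and the placebo-controlled tables up to Week 12 cannot be reached by this route.
- **Link with efficacy.** It is tempting to say that the most effective arms are inflated most. Suppose 5% to 25% of subjects have an AE ongoing at first dose, and its grade falls without resolving in 20% on placebo and 40% on drug. The spurious difference is then 0.05 x (0.40 - 0.20) = 1 point to 0.25 x (0.40 - 0.20) = 5 points. All these rates are assumed. Equal rates give zero, and a dose that resolves more AEs completely would leave fewer lower-grade records and could reverse the sign. The documents do not support a direction.
- **The AE definition.** It introduces new or aggravated occurrences as things included, so it is not strictly a limit. The two protocol statements sit badly together but are not a flat contradiction.
- **The start date.** No section says that the separate record carries a new one, and the eCRF instructions are not among the documents.
- **Other safeguards.** No p-values are planned for AEs (SAP 12.1.6). The treatment-related tables take a record only if it is rated at least possibly related or its relatedness is missing (12.1.2). A fall in grade cannot create a false severe TEAE. The listings show start dates and onset days, so cases could be found.

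None of this changes the outcome of cases A and C for a programmer who follows SAP 12.1.1 as written.

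**Conclusion.** The point holds in a limited form. Given a new start date for the separate record, an AE ongoing at first dose that eases without resolving is misclassified as a TEAE in both the Week 12 and the full-24-week tables. An AE ongoing at Week 12 that eases later gets an unwarranted entry in the second-12-weeks tables of its own sequence column.

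The size is about 1.4 percentage points per affected subject in a preferred-term row at n = 70, and less on average in the any-TEAE row. The number of affected subjects and any imbalance between arms cannot be derived from the documents. The change is worth making because the misclassification is systematic, reaches tables used for dose selection, and is cheap to remove.

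**What to change.** In SAP 12.1.1, keep new-onset events on or after first dose as TEAEs and add a rule for intensity-change records:

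1. Count such a record as treatment-emergent only if its intensity exceeds the worst intensity of the same AE before first dose.
2. Count it in the second 12 weeks only if its intensity exceeds the worst intensity of the same AE up to the Week 12 visit.
3. Link records by preferred term and contiguous dates, and review the links blinded before database lock.
4. Keep lower-intensity records in the listings, shown under the original onset.
5. Reconcile the protocol's intensity-change rule with its AE definition, and state which start date the separate record carries.

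The comparison should be with the worst earlier intensity, not with the record immediately before. Under the latter, an AE that is moderate before dosing, then mild, then moderate again would count as emergent without ever exceeding its pre-dose grade.

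The cost is SAP wording, one derivation and some review time, with some risk of linking events that are truly separate. SAP 6.3.2 shows that this SAP version post-dates the interim lock. The change would therefore reach the final tables, and interim AE tables would have to be re-run to match.
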